[USE THIS BIOMEDICAL PROTOCOL TEMPLATE IF YOUR PROJECT INVOLVES ANY PHYSICAL CONTACT OR MEDICAL INTERVENTIONS WITH PARTICIPANTS]

INSTRUCTIONS:

- Use this template to prepare a document with the information from the following sections.
- Depending on the nature of what you are doing, some sections may not be applicable to your research. **Do not delete any sections, questions, or help text and mark "N/A" if sections do not apply**
- When you write a protocol, keep an electronic copy. You will need to modify this copy when making changes.

PROTOCOL TITLE:

*Intervention Pilot with Parents of Technology-Dependent Children
(Modified 6/1/18 and approved by UHCMC IRB)*

PRINCIPAL INVESTIGATOR:

*Name- [name], RN, CPNP
Primary Department- CWRU FPB School of Nursing
Telephone Number- [contact]
Email Address- [contact]*

UH FACULTY ADVISOR:

If the principal investigator's primary role at UH is resident, fellow or student, identify a faculty advisor.

*Name N/A
Primary Department
Telephone Number
Email Address*

OTHER DEPARTMENTS INVOLVED IN THIS STUDY (IF APPLICABLE):

Pulmonology- [name] is the UH Sponsor

VERSION NUMBER:

Include the version number of this protocol if assigned by an outside entity.
I am not sure of the version number.

DATE:

Include the date of submission or revision.
It is the current version as of May 21, 2018

Objectives

1. Describe the purpose, specific aims, or objectives.
2. State the hypotheses to be tested.

Purpose: The purpose of this randomized clinical trial (RCT) is to test the efficacy of a Resourcefulness Training intervention designed for 94 parent (male and female) caregivers of technology-dependent children on the parents' psychological and physical outcomes and on family outcomes at 6 weeks, 3 months, and 6 months post-intervention.

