3. Describe the criteria that define who will be **excluded** in your final study sample.

	Exclusion
1.	Parents of children with cancer.
2.	
3.	
4.	

Number of Research Participants

1. *Indicate the target number of research participants to be accrued locally.*
2. *If this is a multi-site study, indicate the total number of research participants to be accrued across all sites.*

For this study, 123 subjects are expected to be enrolled.

Vulnerable Populations

1. *Indicate specifically if you will include each of the following special populations by checking the appropriate box:*

- Adults unable to consent**
- Minors (infants, children, teenagers)**
 - Wards of the state
 - Foster Children
- Pregnant Women**
- Neonates**
- Neonates of Uncertain Viability**
- Employees of CWRU or UHHS**
- Prisoners**
- Illiterate Individuals**
- Non-English Speaking**
- University Students**

2. *If the research involves individuals that are included in a vulnerable population, describe the additional safeguards included to protect the rights and welfare of the individuals for each population indicated.*

We will include pregnant women or women who become pregnant while enrolled in the study because many mothers of technology-dependent children are in the child-bearing years. They will be told that they are volunteers and can leave the study at any time. While we will not be directly asking the children any questions we will be asking their parent to describe things such as what type of technological equipment they use and questions about their eating and sleeping. Therefore, we have a procedure for asking about the child's assent if they are 7 years or older.

3. *If excluding pregnant women, illiterate or non-English speaking individuals, provide a scientific rationale for the exclusion. Inconvenience or cost is not an acceptable rationale.*

We will exclude illiterate or non-English speaking individuals due to the amount of reading, writing that must be done as part of the intervention and follow up data collection. Also, our instruments have not been translated into another language.

Recruitment Methods

1. *Describe the source of the research participants.*
2. *Describe the methods that will be used to identify potential research participants.*

3. *Justify the feasibility of recruiting the required number of suitable research participants within the agreed recruitment period. For example, how many potential research participants do you have access to?*

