Research Design. A quasi-experimental RCT design with random assignment will be used to test the efficacy of a Resourcefulness Training (RT) intervention compared with an attention control group in mothers and fathers of technology-dependent children. All participants will receive a face-to-face visit from study staff for the T1 data collection. In addition, the intervention group will receive individually tailored RT web based instruction via an approximately 30 minute video that provides details on each of the 8 resourcefulness skills with short examples of application, instruction on journal writing to practice and reinforce use of resourcefulness skills, access to video tapes of parents describing application of resourcefulness skills in the care of their technology-dependent child. Parents will be asked to provide their email address so that we may send them invitation for access to the website that they may visit at any time to access the video tapes. Data will also be collected face-to-face at 3 months (T3) and 6 months (T4) post-intervention. At 6 weeks parents will be emailed a link to the REDCap survey for Time 2 data collection and contacted by phone for SF-12 survey with email reminders. Open-ended questions following their final data collection appointment will allow mothers/fathers to discuss feasibility, acceptability, and fidelity of this intervention and suggestions for potential modification of the intervention and follow up procedures. For this study, 99 female participants and 24 male participants are expected to be enrolled that takes into account 10% attrition.

Measures/Instruments.

The **Depressive Cognition Scale** an 8-item scale ($\alpha = .75$), will measure depressive thought patterns that may lead to depression.⁸ Responses on a 6-point scale range from strongly agree (5) to strongly disagree (0) with a score range 0-40. Items include depressive cognitions such as hopelessness and worthlessness; higher scores indicate more depressive cognitions.

The **Resourcefulness Scale**, a 28-item scale ($\alpha = .85$), will assess both personal (16 items) and social (12 items) resourcefulness.⁹ Responses on a 6-point scale range from extremely descriptive (5) to not descriptive (0) with a score range 0-140; higher scores indicate greater resourcefulness. Construct validity was assessed using confirmatory factor analysis.

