After confirming the child's assent and obtaining the participant's written informed consent, the participant will be assigned a code number. Mothers/fathers will be randomly assigned to one of two treatment conditions- Resourcefulness Training intervention or Attention Control using the Minim computerized method of random assignment based on parent gender, child's type of technology (mechanical ventilation or intravenous medication/nutrition, all others), race ethnicity (White non-Hispanic, all others). Data collection will take place in a private place of the mother's/father's choosing such as her/his home. The instruments should take about 50 minutes to complete at initial enrollment but thereafter it should take about 30 minutes (Table 1). After the participant has completed the self administered questionnaires, the interviewer will score the CES-D. If the total score of the CES-D exceeds the cutoff of 16 for depressive symptoms the participant will be notified and the information regarding mental health resources will be given-(see additional files). Following T1 data collection, mothers/fathers will receive either intervention or attention control protocol according to their random assignment. The RT intervention which includes instruction on maintaining a 28 day journal will take about 45-50 minutes to review with participants. At T4, one additional questionnaire, Resourcefulness Skills Scale, will be given to the Resourcefulness Training intervention group only to assess for intervention fidelity. Reminder post cards will be sent as needed. A \$25 gift card will be given following completion of questionnaires at each of four time points. Following completion and submission of all questionnaires and the RT journals, participants will be interviewed via speaker phone to determine the feasibility, acceptability and fidelity of the intervention. Telephone interviews will take place at a time convenient for the participant and will be audio-recorded. In order to aid in retention, participants will be mailed birthday cards on the parent's and child's birthdays as well as monthly postcards with an inspirational message and contact information for the study office. The **RT intervention** group will be taught RT skills and mnemonic strategies (acronyms, practice) to facilitate recall of RT skills using a web based program that includes a video approximately 32 minutes long. The 8 letters in the acronym **RESOURCE** will be used to prompt recall: **R**ely on family/friends; **E**xchange ideas with others; **S**eek professionals or experts; **O**rganize daily activities; **U**se positive self-talk; **R**eframe the situation positively; **C**hange from usual reaction; **E**xplore new ideas. Practice of RT will occur through using a personal semi-structured journal (example in other study documents) to daily record which resourcefulness skills were used that day as well as one's thoughts and feelings related to specific situations in which the resourcefulness skills were used. As intervention reminder tools mothers/fathers will be given a laminated card to keep in their journal as well as a magnet to

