Hair sample for cortisol level, audio recording with only subject ID number for exit interview regarding intervention for intervention group only. Questionnaires will be administered as well.

Data Analysis Plan

1. *Describe the data analysis plan, including any statistical procedures. Provide a power analysis if applicable.*
2. *If applicable, describe the primary and secondary study endpoints including safety endpoints.*

ANALYSIS. All data will be entered into UH REDCap and cleaned. We hypothesize that parents receiving the Resourcefulness Training intervention will have significant improvement in parental outcomes (psychological and physical) and family outcomes (family functioning) compared with parents in the Attention Control arm. We also hypothesize that resourcefulness will mediate the effect of the intervention on all study outcomes.

Preliminary Analyses. Exploratory data techniques will be used to examine univariate characteristics (central tendency, dispersion, and distribution) of demographics and covariates measured upon randomization in each arm. These exploratory techniques will be based on proportions (in the case of dichotomous variables) and medians and/or means (in the case of variables measured on an interval scale). Due to randomization, no formal tests of these variables will be performed because any imbalance between arms is known to be due to chance. Profile plots will also be used to describe the participant-specific (parent) and arm-specific trends for each outcome over the four time points.

Primary Analyses.

Aims 1 & 2: Analysis of the monthly rate of change in each of the parent outcomes in each arm will be estimated via linear mixed models and fit using SAS PROC MIXED.108,109 Each model will include a random intercept and slope (possibly modeled using a polynomial spline) to account for between-subject variance in each outcome over time. Conditional on these random effects, we will also explore within-subject variance in

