each outcome over time using different residual covariance structures and select the most appropriate structure using likelihood-based criteria. Fixed effects will include a continuous variable to represent time since randomization, an indicator variable to represent the intervention, and stratification factors used during randomization (facility, OTA technology group, sex and race/ethnicity). Assuming a linear rate of change over time, the regression coefficient of the terms representing interactions between time and the intervention indicator variable will be used to estimate the difference in the monthly rate of change in each outcome between the two arms.

To determine if resourcefulness mediates the effect of the resourcefulness intervention on parent outcomes, a model-based causal mediation model^{110,111} will be fit using separate generalized linear models of parent outcomes at 3 months after randomization that adjust for the intervention indicator variable, stratification factors, and the mediator at 6 weeks after randomization. This model will allow us to decompose the total effect of the resourcefulness intervention on maternal outcomes at 3 months into direct and indirect (or mediated) effects and will allow us to estimate the proportion of the total effect that is mediated. Variance estimates, and consequently 95% confidence intervals, will be estimated using a bootstrapping procedure based on 1000 bootstrap samples. To more fully explore the temporal pattern of mediated effects, we will use similar models to also estimate the mediated effect using measurements of the mediator and maternal outcome taken at other time points as well (e.g., total effect of resourcefulness intervention on parent outcomes at 6 months that are mediated by personal or social resourcefulness at 3 months).

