To account for any multiple comparisons, a Bonferroni-corrected two-sided significance level will be applied to all analyses for all aims. Additionally, as with any study, we expect some level of missing data at each time point. To adjust for the missing data in all mixed-models analyses, we will use pattern-mixture models. This modeling approach will be applied to each model to ensure that missing data is adequately accounted for in each analysis. In contrast to a “completers only” approach, pattern-mixture models will provide a consistent and asymptotically efficient estimate of the effect of intervention on the monthly rate of change in parent and family outcomes when data is missing not at random.

Secondary Analyses. To obtain more precise estimates of the intervention effect on the time point interval rate of change in each parent or family outcome, additional multivariable analyses will characterize and estimate the relationship between potential covariates at baseline and each outcome. For continuous variables that do not have a linear relationship with the outcome, appropriate transformations or categorization will be considered. For nominal and ordinal variables, the number and type of categories will be considered to obtain

the optimum relationship, if any, with the outcome. Based on a two-sided significance level of 0.15, any baseline covariate found to be associated with the outcome will be included in the model described for the Primary Analyses.

Modification of the intervention effect on the monthly rate of change in each parent outcome will also be tested in each model by including an interaction between a pre-specified effect modifier measured at baseline, the intervention indicator variables, and the variable representing time since randomization. Should an interaction be detected based on a two-sided significance level of 0.05, the monthly rate of change in each outcome will be estimated in each of the arms for each level of a categorical effect modifier or at the 25th, 50th, and 75th percentiles of a modifier that is measured on an interval scale.

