Annual assessments of new literature in the field that may have an impact on the safety of participants or on the ethics for the research study will be conducted by the graduate student research assistant under the oversight of the PI and Co-Is. The PI and Co-Is will evaluate this new information for its bearing on all aspects of this research project. This information and the team’s analysis will be disseminated to the SMC at least annually, or sooner if important external factors or relevant information is identified that impacts subject safety or raises ethical concerns. In addition, at each committee meeting, SMC members also will be queried about new studies or ethical issues that they think should be discussed or reviewed, and these items put on the SMC meeting agenda.

f. Advanced Plans for Interim or Futility Analysis

This research project compares the psychological and physical outcomes of Resourcefulness Training against Attention Control in parents caring for technology-dependent children at home. The study investigators anticipate a medium effect size for these interventions; given this expectation and the low risk nature of the study, no formal “futility analysis” will be conducted. However, data summaries will be reviewed by the SMC every six months and interim analyses will be conducted as recommended by the SMC.

Drugs or Devices

There are no drugs or devices being utilized in this research project – *please leave rest of this section blank*

1. *If the research involves drugs or device(s), describe your plans to store, handle, and administer those drugs or device(s) so that they will be used only on research participants and be used only by authorized investigators.*
2. *How will the drug(s) be dispensed (i.e., indicate the pharmacy that will be used)?*
3. *If the drug is investigational (has an IND) or the device has an IDE or a claim of abbreviated IDE (non-significant risk device), identify the holder of the IND/IDE/Abbreviated IDE*

Additional Information

If you have any additional information regarding your study not covered in the template, please include it here.

Community-Based Participatory Research

- This is not a community-based participatory research project – *please leave rest of this section blank*

If applicable, describe the involvement of the community in the design and conduct of the research.

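### The proportion mediated is planned whatever the size of the total effect and with bootstrap-variance intervals, which are unstable here unless total effects are clearly larger than medium

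*Combined protocol and SAP*

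**What the plan says.** The mediation paragraph of the Primary Analyses (Data Analysis Plan) models outcomes at 3 months, with resourcefulness at 6 weeks as mediator. It splits the total effect into direct and indirect parts and will also "estimate the proportion of the total effect that is mediated". Variances, and from them 95% intervals, come from 1000 bootstrap resamples. Similar models are planned at other visits.

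The hypothesis at the start of the Data Analysis Plan is broad: "We also hypothesize that resourcefulness will mediate the effect of the intervention on all study outcomes". Aim 1 names eight outcomes. The mediation paragraph itself speaks of parent and maternal outcomes.

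On size, the Research Design text says "99 female participants and 24 male participants are expected to be enrolled that takes into account 10% attrition". On effect, section f (interim or futility analysis) says only "The study investigators anticipate a medium effect size for these interventions".

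The documents do not tie the proportion to the presence of a total effect, name percentile limits, or say how values below 0 or above 1 will be handled. The mediation sensitivity analysis under Secondary Analyses concerns unmeasured confounding and is judged on the significance of the mediated effect, not on this ratio.

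**The concern.** A ratio behaves badly when its denominator is not well separated from zero. If the total effect is within two or three standard errors of zero, some of the 1000 resamples give a denominator close to zero or of the wrong sign. The ratio in those resamples can be huge or negative, and a few of them can dominate the bootstrap variance. An interval built from that variance is then too wide and changes with the seed.

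The risk is a quoted percentage mediated that carries little information, or a plausible-looking percentage for an outcome the intervention did not change. The Background says the results are meant to inform a larger study, so such a figure could be carried into its design.

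**Working it through.** **Inputs from the documents.** Enrolment is 99 + 24 = 123. With 10% attrition, 123 × 0.90 = 110.7, so 110 or 111 completers. There are two arms (parents are "randomly assigned to one of two treatment conditions") and 1000 resamples. The plan gives no figure for mediation precision, so there is none to reproduce.

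**Assumptions.** 1:1 allocation; outcome SD of 1; linear models; an effect on the mediator of 0.5 SD (0.8 gave similar results); medium taken as 0.5 SD, with 0 to 0.8 SD shown.

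**Step 1: distance of the denominator from zero.** The standard error of the total effect is √(4/N) = √(4/111) = 0.190 SD.
- 0.3 SD: 0.3/0.190 = 1.6 standard errors
- 0.5 SD: 0.5/0.190 = 2.6
- 0.8 SD: 0.8/0.190 = 4.2

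The Objectives describe a study "designed for 94 parent (male and female) caregivers of technology-dependent children". With N = 94 the standard error is √(4/94) = 0.206, and 0.5/0.206 = 2.4. That mismatch with 123 is a separate matter; results at 94 are similar or worse.

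**Step 2: what this does to the resamples.** At N = 111 the estimated total effect falls below zero with probability 0.004 at 0.5 SD and 0.055 at 0.3 SD. A trial that observes exactly those effects would have roughly 0.004 × 1000 = 4 and 0.055 × 1000 = 55 resamples with a reversed denominator, and others close to zero.

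**Step 3: simulation at N = 110, true proportion 40%.**
- 0.5 SD: the variance-based interval contains all of 0-100% in 62%, 67% and 68% of trials in repeated runs. With 300 trials the Monte Carlo standard error is √(0.65 × 0.35/300) = 2.8 points, so these agree. Two seeds give bootstrap SDs more than 2-fold apart in 36-44% of trials. Median width is about 3.5 for variance-based and 1.1 for percentile limits. Percentile limits contain all of 0-100% in 31%.
- 0.3 SD: the variance-based interval contains 0-100% in 88-89% of trials, seeds differ more than 2-fold in 53%, and 17-22% of point estimates lie outside 0-100%.

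**Step 4: the same at N = 111 over a range of effects.** Estimates outside 0-1 come from 20,000 trials per row. The other columns are medians over 200 data sets, each bootstrapped with five seeds of 1000 resamples. A width of 1 is 100 percentage points.

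| Total effect (SD) | True proportion | Estimates outside 0-1 | Bootstrap SD of ratio, max/min over seeds | Width, variance-based | Width, percentile | Bootstrap SD of indirect effect, max/min |
|---|---|---|---|---|---|---|
| 0 | none | 58% | 8.7 | 33.9 | 5.4 | 1.07 |
| 0.3 | 0.5 | 21% | 8.5 | 28.7 | 4.4 | 1.06 |
| 0.5 | 0.5 | 8% | 5.1 | 4.1 | 1.35 | 1.06 |
| 0.5 | 0.3 | 3.5% | 4.3 | 2.3 | 0.85 | 1.06 |
| 0.8 | 0.3 | 0.5% | 1.1 | 0.52 | 0.50 | 1.06 |

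The fault is specific to the ratio. In the same data sets the indirect effect hardly depends on the seed.

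**Step 5: would a significance condition help?** Reporting the ratio only when the total effect is significant keeps the trials with overestimated denominators. With a true 40%, the median reported proportion at 0.3 SD is 24-26% (condition at 0.05) or 20% (at 0.05/8 = 0.00625). At 0.5 SD it is 36% or 33%. At 0.5 SD (N = 111, true proportion 0.5), the bootstrap SD still differs about 2.2-fold over five seeds among trials passing at 0.00625.

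**The case against.** The best defence is that the ratio is a minor quantity. Aim 2 asks whether mediation occurs. The plan lists direct and indirect effects before the proportion, and its sensitivity analysis judges mediation on the mediated effect. This stands: a reader might infer that percentages are the planned headline of Aim 2, but the documents do not say so, and Aim 2 can be answered without the ratio.

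A reader might also infer that the percentages are bound to be uninterpretable. That goes too far. At an assumed 0.5 SD, 92-96% of point estimates lie within 0-100%, and at 0.8 SD the ratio is mostly usable. The plan gives no numeric effect size, so neither case can be excluded.

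Third, no interval formula is given. The wording favours intervals computed from the variance but does not rule out percentile limits, whose width varies only about 1.2-fold across seeds at 0.5 SD. So it is the variance that lacks a stable value, not every bootstrap summary. If percentile limits were intended, the change is a clarification, though the limits stay wide.

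Finally, reporting the proportion only after a significant total effect is a natural remedy. Step 5 shows its bias. It would also need a defined level, and the plan says only that "a Bonferroni-corrected two-sided significance level will be applied to all analyses for all aims", with neither base level nor divisor.

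**Conclusion.** The point holds in limited form. The proportion mediated is planned with no regard to the total effect, and its intervals are described as following from bootstrap variances. With about 110 completers, that interval is inflated and seed-dependent unless total effects are clearly larger than medium. At 0.5 SD it contains the whole 0-100% range in about two thirds of trials, and percentile limits cut its median width from about 3.5 to 1.1. At 0.3 SD about a fifth of point estimates are impossible as proportions. Small effects deserve weight because eight outcomes are unlikely all to show a medium one: at N = 111, power for a 0.3 SD total effect is 35% at a two-sided 0.05.

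These sizes rest on the assumed effect sizes, 1:1 allocation, the assumed mediator effect and no missing data beyond the 10%. The direction does not depend on their exact values. Neither the indirect effect nor the ability to answer Aim 2 is in doubt.

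**What to change.** Amend the mediation paragraph of the Primary Analyses in three ways:

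1. Replace variance-based intervals with percentile bootstrap limits for the mediation quantities, from the same 1000 resamples.
2. State that the Aim 2 conclusion rests on the indirect effect in outcome units with its percentile interval, in line with the sensitivity analysis under Secondary Analyses.
3. Label the proportion mediated as descriptive. Show it for every outcome analysed, always beside the total effect and its 95% interval, and do not interpret it where that interval includes zero.

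Do not make reporting conditional on a significant total effect. Showing every proportion avoids selective reporting, but the subset whose total-effect interval excludes zero will still tend to understate the true proportion (Step 5), and the text should say so.

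The cost is wording and a small change in code, with no new data and no further resampling. The downside is that, for outcomes with a weak total effect, the proportion appears with very wide limits and supports no conclusion.

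### Aim 2 intervals that follow from a bootstrap variance would be conservative for a mediated effect; percentile limits are a cheap improvement

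*Combined protocol and SAP*

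**What the plan says.** The Primary Analyses part of the Data Analysis Plan fits separate generalized linear models to outcomes at 3 months. These models "adjust for the intervention indicator variable, stratification factors, and the mediator at 6 weeks after randomization". The total effect is split into direct and mediated parts, and on uncertainty the text says: "Variance estimates, and consequently 95% confidence intervals, will be estimated using a bootstrapping procedure based on 1000 bootstrap samples".

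Three other statements bear on how the interval will be used:

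- The opening paragraph of the analysis section states the hypothesis: "We also hypothesize that resourcefulness will mediate the effect of the intervention on all study outcomes".
- The multiplicity paragraph says that "a Bonferroni-corrected two-sided significance level will be applied to all analyses for all aims". It gives neither the base level nor the number of tests.
- The last paragraph of Secondary Analyses plans to find how strong an unmeasured confounder would have to be to make a mediated effect non-significant.

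No other test of the mediated effect is described, so the bootstrap interval serves as the test. No section names a percentile, bias-corrected or normal interval. No section gives a path size, an indirect effect size or a power figure for Aim 2.

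**The concern.** In linear models without an arm-by-mediator interaction, the mediated effect is a × b, where a is the effect of arm on the mediator and b is the effect of the mediator on the outcome given arm. When either path is zero or modest, the sampling distribution of the product is peaked near zero and skewed. An interval of estimate ± z × bootstrap SD ignores that shape, although the resamples already contain it.

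The direction of the error is towards missing mediation, not towards claiming it falsely. Aim 2 is one of the trial's two aims. A method that seldom excludes zero for moderate mediation weakens what the trial can say on that aim, and the data to do better are already in hand.

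**Working it through.** **Inputs from the documents**

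- Resamples: 1000 (Primary Analyses).
- Sample size: the purpose statement describes a training intervention "designed for 94 parent (male and female) caregivers of technology-dependent children". The participant-number section says "For this study, 123 subjects are expected to be enrolled", and Research Design says "99 female participants and 24 male participants are expected to be enrolled that takes into account 10% attrition". These do not reconcile: 94/(1 − 0.10) = 104.4, so 105, while 123 × 0.9 = 110.7, about 111. The check therefore covers n = 94, 111 and 123.
- Effect size: "The study investigators anticipate a medium effect size for these interventions", in the safety-monitoring section, with no number.
- Outcomes and mediators: the aims list eight outcomes and two kinds of resourcefulness.

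**Assumptions**

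Paths a and b in SD units, 1:1 allocation, normal errors with unit residual SD, one mediator, no direct effect and no covariates. Taking a = 0.5 for a medium effect on the mediator is an assumption; the documents attach no size to that path. The plan states no Aim 2 figure, so there is none to reproduce.

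**Why the variance-based test is conservative**

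Let z_a and z_b be the two paths divided by their standard errors. With the first-order variance a²·SE_b² + b²·SE_a², the ratio of estimate to SD is

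z_a·z_b / √(z_a² + z_b²),

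which is always smaller in size than the weaker of the two. If the two are equal, each must reach 1.96 × √2 = 2.77 before the ratio reaches 1.96.

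Example with n = 111, a = 0.5, b = 0.30:

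- SE_a = 2/√111 = 0.190, so z_a = 2.63.
- SE_b = 1/√111 = 0.095, so z_b = 3.16.
- Ratio = (2.63 × 3.16)/√(6.92 + 9.99) = 8.31/4.11 = 2.02.

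Two clearly significant paths only just clear 1.96.

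**Simulated rejection with no mediation** (n = 111, nominal 5%, 2000 trials, 1000 resamples each)

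| a | b | Variance-based | Percentile |
|---|---|---|---|
| 0 | 0 | 0.0% | 0.2% |
| 0.5 | 0 | 0.7% | 3.2% |
| 0 | 0.30 | 1.4% | 3.8% |
| 0 | 0.39 | 2.4% | 5.3% |
| 0 | 0.59 | 4.1% | 6.0% |

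Bias-corrected limits rejected in 6.4% to 8.3% of trials with one path non-zero, above nominal.

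**Simulated power, two-sided 5%** (Monte Carlo standard error about 1 point)

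| n | a | b | Variance-based | Percentile | Loss (points) |
|---|---|---|---|---|---|
| 94 | 0.5 | 0.30 | 30.4% | 52.0% | 21.6 |
| 111 | 0.3 | 0.30 | 14.4% | 28.4% | 14.0 |
| 111 | 0.5 | 0.20 | 17.4% | 36.9% | 19.5 |
| 111 | 0.5 | 0.25 | 29.0% | 51.0% | 22.0 |
| 111 | 0.5 | 0.30 | 40.2% | 60.4% | 20.2 |
| 111 | 0.5 | 0.39 | 58.0% | 71.2% | 13.2 |
| 111 | 0.5 | 0.59 | 70.3% | 74.8% | 4.5 |
| 111 | 0.8 | 0.39 | 91.6% | 96.0% | 4.4 |
| 123 | 0.5 | 0.25 | 35.4% | 60.0% | 24.6 |
| 123 | 0.5 | 0.50 | 74.4% | 80.2% | 5.8 |

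A separate simulation at n = 110 agrees: 45% against 66% at 0.5/0.30, 59% against 71% at 0.5/0.40, 70% against 73% at 0.5/0.60, and 95% against 98% at 0.8/0.40. The overall range is therefore about 3 to 25 points.

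As a plausibility check, when b is strong, power should approach that of the arm-to-mediator comparison alone: 0.5 × √111/2 = 2.63, and Φ(2.63 − 1.96) = 0.75. The 74.8% in the table fits.

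**At a Bonferroni level**

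The family is not stated. Taking 0.05/8 as an assumption, the loss over the grid is 4 to 35 points. At n = 111 it is 24.2 points at 0.5/0.30 (6.0% against 30.2%) and 35.4 at 0.7/0.30 (20.7% against 56.1%). At 0.5/0.20 it falls to 10.3 points (1.4% against 11.7%), because both methods then have little power.

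The planned 1000 resamples leave 1000 × 0.05/(2 × 8) = 3.1 draws in each tail at 0.05/8, and 1.6 at 0.05/16. The percentile figures at 0.05/8 used 1000 resamples and are correspondingly rough.

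**The case against.** The strongest reply is that the defect is inferred. Grammatically, both the variances and the intervals are to be estimated by bootstrapping, and nothing in the text writes ± 1.96 SD, mentions normality or excludes percentile limits. The mediation method is cited to sources numbered 110 and 111, while the reference list ends at 30, so the documents cannot settle what was meant. This stands: the variance-based interval is the natural reading of *consequently*, since percentile limits need no variance, but it is not proven.

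A reader might also infer that the plan gives up 20 or more points of power in general. The documents do not support that. They give no path sizes, and the anticipated medium effect is not tied to resourcefulness as a mediator. In the simulations the loss reaches about 20 points only in a band of moderate paths.

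Nor is the test always far below its nominal level: it rejects in 4.1% of trials when a = 0 and b = 0.59. When both paths are zero, percentile limits are far below nominal too.

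Finally, a conservative interval does not create false mediation claims. The objectives call the work exploratory, and the plan also estimates effect sizes and the proportion mediated. This is a matter of efficiency, not validity, which limits the weight of the point but does not remove it.

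**Conclusion.** The point holds in conditional form. As worded, the plan most naturally yields a symmetric interval built from the bootstrap variance. If that is what is done, the test of mediation is conservative, with about 1% rejection at nominal 5% when one path is zero and the other moderate. It loses about 3 to 25 points of power against percentile limits at the 5% level for n = 94 to 123. The loss is about 20 points for paths near 0.5 to 0.6 and 0.2 to 0.3, and about 3 to 6 points for strong paths. These figures rest on assumed path sizes, normal data, one mediator and no covariates.

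The sentence needs work under the other reading too. If percentile limits were intended, 1000 resamples are too few for a Bonferroni tail, and a 95% interval does not match the corrected level. This is a cheap improvement, not an error that invalidates the analysis.

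**What to change.** In the mediation paragraph of Primary Analyses, replace the bootstrap sentence with:

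> Confidence limits for the direct, indirect and total effects will be the percentiles of the bootstrap distribution at the (Bonferroni-corrected) level used for the test, with enough resamples (for example, at least 10,000) for stable tail percentiles; they will not be computed from the bootstrap variance.

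With 10,000 resamples each tail holds about 31 draws at 0.05/8 (10,000 × 0.003125) and about 16 at 0.05/16. The number of tests in the Bonferroni family has to be written down for this level to be defined. Naming percentile limits also rules out a later choice of bias-corrected limits, which exceeded the nominal level in the check above.

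The cost is asymmetric limits and slightly more computing. No new data are needed.
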